### **9.3. Data Definition and Deviations**

#### **9.3.1. Baseline and Change from Baseline**

In general, the last recorded value prior to the first study treatment will serve as the baseline measurement for the safety endpoints such as lab, vital signs, and electrocardiograms (ECGs). The first treatment could be the first dose for PK collection or, if PK dose is not implemented, the first dose during the treatment phase. If there are multiple results collected on the same day, the collection done at later time, with the repeat status, or with a later sequence number will be used.

Change from baseline will be calculated as the post baseline value minus the baseline value. Percentage change from baseline will be calculated as the change from baseline divided by the

baseline value, multiplied by 100. If either the baseline or post-baseline value is missing, then change from baseline and percentage change from baseline will be set to missing.

### 9.3.2. Study Day and Duration

Study day is relative to the start date of the first treatment of the treatment phase. As stated above subjects may have the first dose for intensive PK purpose prior to the first treatment of the treatment phase. In such cases the study day will not align with the very first dose subjects received. It is set up this way to be consistent with the protocol “Day” definition and to avoid confusion in the listings when the study day is used. There is no study Day 0 defined.

- For an assessment that occurred on or after the study treatment:  
Study day = Date of assessment – date of first study treatment in treatment phase + 1
- For an assessment that occurred prior to the study treatment:  
Study day = Date of assessment – date of first study treatment in treatment phase

A duration between any two dates (such as AE duration) expressed in days will be calculated using the following conventions: Duration = later date – earlier date + 1.

## 10. SUBJECTS BASELINE CHARACTERISTICS, DEMOGRAPHICS AND MEDICATIONS

### 10.1. Subject Disposition and Withdrawals

Subject disposition will be summarized for all screened subjects. The summary for the screened population will include number of subjects who received at least one study treatment and who were screen failures.

Disposition summary will be based on the safety evaluable population. The following categories will be presented: treatment discontinuation and reasons, study discontinuation and reasons.

Number of subjects received Cycle 1 day 1 dose, included, and not included in the response evaluable population (both definitions) and reason for exclusion will be summarized.

### 10.2. Protocol Deviation

Protocol deviations were collected in the protocol deviation log. Major protocol deviations will be summarized by site and by deviation categories. All deviations, both major and minor, will be listed. Major protocol deviations are those in the deviation log that had a level classified as “Level 2”. All the other deviations will be classified as minor protocol deviations.

### 10.3. Demographics and Other Baseline Characteristics

All demographic and baseline characteristic data will be summarized using descriptive statistics for safety evaluable population.

The summary table for demographics and baseline characteristics will include the following information:

- Age (years), age category (<65,  $\geq$ 65 years)
- Sex (male, female)
- Ethnicity (Hispanic or Latino, not Hispanic or Latino)
- Race (eCRF collected race. If more than one race was checked it will be reported as “Other”)
- Weight (kg) and height (cm) collected at baseline
- World Health Organization (WHO) performance status at baseline

Baseline cancer characteristics will include the following:

- Time since initial cancer diagnosis (months)
- Stage at screening

Prior cancer treatment includes prior anti-cancer therapy, prior radiotherapy, and prior surgical procedures. If there are more than one prior anti-cancer therapy collected for a subject, the last one (based on regimen start date) will be summarized including the following:

- Received prior anti-cancer therapy
- Line of Therapy (1, 2, 3, 4, 5, 6+)
- Reason for discontinuation of anti-cancer therapy (CRF terms)
- Prior radiotherapy (yes, no)
- Prior surgical procedures (yes, no)

### 10.4. Medical History and Concomitant Diseases

Medical history was not coded. Details of each medical history will be listed for the safety evaluable population.

## 10.5. Prior and Concomitant Medication

Prior and concomitant medications will be summarized for the safety evaluable population. Medications will be coded using the World Health Organization (WHO) Drug B2-Sept 2016 version. These medications will be further classified as follows.

- Prior medication is defined as those medications that started prior to the study treatment (collected within 28 days prior to the first dose). If medications started prior to the study treatment and were ongoing after the study treatment, they will be considered as both prior and concomitant medications.
- Concomitant medication is defined as those taken on or after the study treatment. If medications started prior to the study treatment and were ongoing after the study treatment, those medication will be considered as concomitant medication as well.

If a medication's start date is completely missing, it will be counted in both prior and concomitant summaries. The number and percentage of subjects taking prior and concomitant medications will be summarized by Anatomical Therapeutic Chemical (ATC) Levels 2 and preferred terms (standardized drug name) by descending frequency based on all the subjects in the population.

## 11. EFFICACY ANALYSIS

Unless specified otherwise all efficacy analyses will be based on the response evaluable population. An alternative definition of response evaluable population is defined in [Section 8.2](#) and additional efficacy summaries may be repeated using the alternative definition if the differences are deemed clinically meaningful.

### 11.1. Overall Response

#### 11.1.1. Overall Response Rate

Overall response rate will be assessed by the investigator per RECIST criteria version 1.1. Partial or complete response should be confirmed by a repeat tumor imaging assessment not less than 4 weeks from the date the response was first documented. The confirmed responses will be derived based on the overall responses by timepoint using the logics below:

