3.2 DESIGN OF THE CLINICAL TRIAL

This is a multicenter, first-in-human, Phase 1/2, open-label, dose-escalation trial in subjects with advanced solid tumors or non-Hodgkin lymphoma (NHL), with cohort-expansion phase in 6 indication-specific expansion cohorts (Figure 6). The trial will consist of 2 stages:

- Stage 1: A Dose Escalation Phase.

It is expected that between 30 and 50 subjects with solid tumors or NHL will be enrolled in the Dose Escalation Phase of the study.

Intensive PK and ECG monitoring for QTc assessments will be collected from all enrolled subjects, beginning with sampling before and after a single dose of SRA737 given on one day between Day -7 and Day -4. Tissue (archival or fresh) and blood will be collected for retrospective biomarker analyses.

Cohorts consisting initially of a single subject will receive escalating doses of SRA737, starting in Cohort 1 with 20 mg/day administered orally on a continuous daily dosing schedule in 28-day cycles. The dose will be escalated until the MTD has been identified, unless determined otherwise by the Sponsor in consultation with the Chief Investigator, for example, if an alternative schedule is pursued instead.

Once a SRA737-related, Grade 2 toxicity is observed in a dose escalation cohort during Cycle 1, that cohort will be expanded to 3 to 6 subjects, and subsequent dose level cohorts will follow a rolling 6 design. See Section 3.3 for additional details.

Dose escalation with an alternative schedule may begin at any time and may either run in parallel or instead of continued escalations in the continuous schedule.

The final number of subjects enrolled into the trial is dependent on the number of dose levels explored in the Dose Escalation Phase.

- Stage 2: A Cohort Expansion Phase.

Approximately 120 subjects will be enrolled into the Cohort Expansion Phase which consists of 6 indication-specific expansion cohorts of approximately 20 prospectively-selected genetically-defined subjects each (namely, subjects with previously treated metastatic CRC, HGSOC without *CCNE1* gene amplification, HGSOC with *CCNE1* gene amplification (or alternative genetic alteration with similar functional effect), mCRPC, advanced NSCLC, and HNSCC/SCC). This allows for a preliminary exploration of the efficacy of SRA737.

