11.2.3 EFFICACY ANALYSES

The analysis of all efficacy endpoints will be based on the Response Evaluable Population.

Efficacy endpoints will be evaluated using RECIST v1.1 criteria, or for subjects with NHL, the revised IWG criteria ([Cheson 2007](#)), or for subjects with mCRPC, a composite response rate defined as any one of the following ([Scher 2016](#)):

- Best response based on RECIST v1.1
- PSA decrease of $\geq 50\%$

- CTC count conversion

Absolute values for PSA and CTCs will be recorded at baseline and response will be analyzed based on percentage of change.

Descriptive analyses of the distribution of ORR, DCR, DOR, TTR, TTP, PFS per RECIST v1.1, the revised IWG criteria, or a composite of any one of the following:

A) Response based on RECIST v1.1; B) PSA decrease of $\geq 50\%$; or C) CTC count conversion, as applicable, and OS will be prepared.

The ORR will be summarized using binomial proportions and confidence intervals computed by the method of Wilson. The examples below display the CI estimates for response within each indication-specific group of approximately 20 enrolled to an expansion cohort. i.e. at the 95% CI, 0 of 20 responses observed excludes an ORR of 16%.

Numerator	Denominator	Proportion	Lower	Upper
0	20	0	0	0.161
1	20	0.05	0.009	0.236
2	20	0.10	0.028	0.301
3	20	0.15	0.052	0.360
4	20	0.20	0.081	0.416
5	20	0.25	0.112	0.469
6	20	0.30	0.145	0.519
7	20	0.35	0.181	0.567
8	20	0.40	0.219	0.613
9	20	0.45	0.258	0.658
10	20	0.50	0.299	0.701
11	20	0.55	0.342	0.742
12	20	0.60	0.387	0.781
13	20	0.65	0.433	0.819
14	20	0.70	0.481	0.855
15	20	0.75	0.531	0.888
16	20	0.80	0.584	0.919
17	20	0.85	0.640	0.948
18	20	0.90	0.699	0.972
19	20	0.95	0.764	0.991
20	20	1	0.839	1

The distribution of DOR, in the subset of subjects responding will be summarized using Tukey's five number summary, including the minimum, mean, median, maximum and

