APPENDIX 2. ASSESSMENT OF DISEASE RESPONSE

Assessment of disease response in this study should be performed according to the RECIST criteria ([Eisenhauer 2009](#)) or for any subject with NHL, using the revised International Working Group (IWG) criteria ([Cheson 2007](#)).

Revised RECIST guideline (v 1.1)

Note that this is an abridged version of the RECIST criteria. Please refer to the Eisenhauer 2009 article for detailed appendices and if in doubt.

Measurability of tumor at baseline

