**Table 3: Confirmed Response per RECIST 1.1**

Initial Response	Subsequent Timepoint	Confirmed Response
Complete Response (CR)	CR at least 4 weeks after initial CR (or consecutive CRs with at most one NE in between with the last CR at least 4 weeks after initial CR)	CR
	CR less than 4 weeks	SD

Initial Response	Subsequent Timepoint	Confirmed Response
	PD or Not Evaluable (NE) or no subsequent assessment	SD if CR is at least 6 weeks from Cycle 1 Day 1, otherwise PD or NE
Partial Response (PR)	PR/CR at least 4 weeks after initial PR (or consecutive PRs/CRs with NEs in between with the last PR/CR at least 4 weeks after initial PR)	PR
	PR/CR less than 4 weeks, or SD	SD
	PD or NE or no subsequent assessment	SD if PR is at least 6 weeks from Cycle 1 Day 1, otherwise PD or NE
Stable Disease (SD)	PD or NE, SD, or no subsequent assessment	SD if SD is at least 6 weeks from Cycle 1 Day 1, otherwise PD or NE
Progressive Disease (PD)	Any assessment or no subsequent assessment	PD

The best overall confirmed response will be the best confirmed response from the above following the order of CR > PR > SD > PD > NE

The best overall response will be summarized for the following endpoints with count and percentage:

- CR
- PR
- SD
- PD
- NE
- ORR (CR + PR) with 95% CI (Wilson method [1])
- DCR (CR + PR + SD) with 95% CI (Wilson method)

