## 11.2. Time to Progression (TTP)

Time to progression is defined as time from the Cycle 1 Day 1 to the earliest date of radiographic disease progression per RECIST 1.1. If a subject did not experience progressive disease, TTP is censored at the last imaging assessment. TTP will be analyzed using the Kaplan-Meier method. The output will include count and percentage of subjects with events or censored outcome including the type of event and censoring. Median TTP and 95% CI based on log-log

transformation will be provided. Landmark analyses at various timepoints may be carried out if of clinical interest. Kaplan-Meier plot supporting the table summary may also be generated.

In addition to TTP by RECIST 1.1 criteria based only on the radiographic assessments, a second definition of TTP which incorporates the clinical progression will be used. The clinical progression is based on the medical review of the reasons of treatment discontinuation or study continuation. If a subject is considered having clinical progression the date of treatment or study discontinuation will be used as date of clinical progression and the TTP is defined as time from Cycle 1 Day 1 to the earliest date of clinical or radiographic disease progression.

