### 11.3. Progression-free Survival (PFS)

Progression-free survival is defined as time from Cycle 1 Day 1 to the earliest date of radiographic disease progression per RECIST 1.1 or death, whichever happens first. The detailed event and censoring rules are shown in the table below following the hierarchical order of the logic:

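### SAP 11.1.1, 11.2 and 11.3 apply RECIST 1.1 to every subject, although the protocol assigns the revised IWG criteria to NHL subjects, and SAP Section 13 does not declare the change

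*SAP*

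**What the plan says.** **Protocol.** NHL is eligible in dose escalation; Section 3.2 expects that "between 30 and 50 subjects with solid tumors or NHL will be enrolled in the Dose Escalation" phase. The criterion for these subjects is stated consistently:

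- Section 11.2.3: "Efficacy endpoints will be evaluated using RECIST v1.1 criteria, or for subjects with NHL, the revised IWG criteria". The same section then names ORR, DCR, DOR, TTR, TTP and PFS as endpoints to be described under RECIST, IWG or the prostate composite, as applicable.
- Appendix 2 repeats the assignment "for any subject with NHL, using the revised International Working Group (IWG) criteria".
- The synopsis and Sections 9.1 and 9.2.2 agree.

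**SAP.** Section 3.1 still describes the population as solid tumors or NHL. The efficacy definitions then name one criterion:

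- Response (11.1.1): "Overall response rate will be assessed by the investigator per RECIST criteria version 1.1", with a single derivation table titled "Confirmed Response per RECIST 1.1".
- TTP (11.2): the event is the "earliest date of radiographic disease progression per RECIST 1.1". A second version adds clinical progression only.
- PFS (11.3): the event is the "earliest date of radiographic disease progression per RECIST 1.1 or death, whichever happens first".
- DOR (11.1.3) borrows the PFS event and censoring rules.

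The only disease-specific response provision, Section 11.1.6, concerns mCRPC. IWG does not appear in the SAP text available for review. Section 13 lists five changes from the protocol, and this is not one of them.

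**The concern.** The two documents give different rules for the same subjects. The SAP rule is stated outright, so this is more than missing detail, and because Section 13 is silent a reader would assume that the protocol rule still stands.

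Any NHL subject also reaches the efficacy outputs. SAP 9.2.1 groups those outputs by tumor type and pools escalation with expansion. SAP Table 1 lists no NHL term under its five indication columns, so a response-evaluable NHL subject would be counted in Other and again in Overall, under a criterion that the protocol does not assign to that disease. The endpoints at stake are ORR, DCR, TTR, DOR, TTP and PFS in those two columns. All are listed among the primary endpoints in SAP 4.1.

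**Working it through.** No figure in the plan rests on this point, so the main check sets the texts side by side.

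| Endpoint | Protocol rule for NHL | SAP rule for all subjects | Conflict |
|---|---|---|---|
| ORR, DCR, TTR | Revised IWG (11.2.3) | RECIST 1.1 (11.1.1, Table 3) | In the stated criterion; possibly not in the input data |
| TTP | Revised IWG (11.2.3) | RECIST 1.1 progression (11.2) | In the event definition |
| PFS | Revised IWG (11.2.3) | RECIST 1.1 progression or death (11.3) | In the event definition |
| DOR | Revised IWG (11.2.3) | PFS rules (11.1.3) | Inherited from PFS |
| OS | Not criterion-dependent | Death (11.4) | None |

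**Response.** SAP 11.1.1 builds confirmed response from the investigator's overall response at each time point; it does not recalculate it from lesion measurements. Protocol 9.3.1 has sites record the applicable response category in the eCRF, and 9.1 directs IWG for NHL. If sites complied, the input to SAP Table 3 for an NHL subject is already an IWG response, and the RECIST title misdescribes it.

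**TTP and PFS.** The event itself is defined as radiographic progression by RECIST 1.1. Two readings are open for an NHL subject whose site declared progression under IWG. The programmer may count that date as the event, against the SAP wording. Or the programmer may look for RECIST progression, find none recorded, and censor at the last imaging assessment (absent death, for PFS). The SAP does not choose.

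**Scale.** The documents give neither the number of NHL subjects nor the size of Other. Reclassifying one subject moves a proportion by 1/n:

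- Other, assumed n = 5: 1/5 = 20 points
- Other, assumed n = 10: 1/10 = 10 points
- Other, assumed n = 20: 1/20 = 5 points
- Other, assumed n = 30: 1/30 = 3.3 points
- Overall, maximum enrolment n = 170 (SAP Section 7): 1/170 = 0.6 points

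The response evaluable set may be smaller than 170, so the shift per subject in Overall is at least 0.6 points.

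**Interval.** The Wilson upper limit is [p + z²/2n + z√(p(1−p)/n + z²/4n²)] / (1 + z²/n), with z = 1.96. It reproduces the table in protocol 11.2.3: 0/20 gives 0.161, and 10/20 gives an interval of 0.299 to 0.701. For zero responders it reduces to z²/(n + z²).

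- n = 10: 0/10 gives 3.84/13.84 = 0.278; 1/10 gives 0.404.
- n = 170: 0/170 gives 3.84/173.84 = 0.022; 1/170 gives 0.033.

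One subject could therefore matter to a small Other column and hardly to Overall.

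**The case against.** The strongest reply is that there may be no NHL subject to misclassify. The SAP was written with study data in view: Table 1 groups verbatim diagnoses from the database, misspellings included, and Section 13 adjusts the disease summaries to actual enrolment. No NHL term appears in those groupings. An NHL subject would also have to be response evaluable under SAP 8.2, through measurable baseline disease, 75% of a cycle, and either a later assessment or a qualifying discontinuation. This stands as a limit on the consequence. It does not settle the matter, because the Other row lists no terms and SAP 3.1 still names NHL. A reader cannot tell an empty category from an undeclared change of criteria.

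A second reply is that ORR and DCR already run on investigator responses, which should be IWG for NHL. The four-week confirmation and six-week stable-disease minimum in SAP Table 3 match protocol 9.2 and 9.3, which make no NHL exception. This also stands, and it reduces the response part of the point to one that may be mainly about labelling. It does not answer the TTP and PFS wording.

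A reader might go further and infer that the reported results are distorted. The documents do not support that. No section shows that an NHL subject was enrolled. The IWG criteria are cited but not reproduced, so the text cannot show that any classification would differ, or in which direction. A reader might also divide an assumed NHL count by the 30 to 50 escalation subjects to express the effect; that count has no source, and escalation is not an efficacy column.

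**Conclusion.** The SAP contradicts the protocol on the response criteria for NHL and does not declare it. That is wrong as written, but it is a minor defect of the plan and not a demonstrated error in results. It is firm for TTP and PFS, and for DOR through PFS, where the event definitions conflict. For ORR and DCR it may be mainly the RECIST label, on the assumption that sites recorded IWG responses as the protocol directs.

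The size is conditional. It is zero if no NHL subject is response evaluable. Otherwise it is 1/n of the column per subject actually reclassified, with the size of Other an assumption throughout. An NHL subject in a column is not necessarily a reclassified one. NHL is not an expansion indication, so the five indication columns are untouched, and so is OS.

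**What to change.** In SAP 11.1.1, 11.2 and 11.3, add that for NHL subjects the time-point response and progression are the investigator's assessments under the revised IWG criteria. DOR then follows through its reference to the PFS rules. Relabel the outputs titled as RECIST 1.1 to match: Tables 14.2.1.1, 14.2.2.1 and 14.2.2.3, Figures 14.2.1.2 and 14.2.1.4, and SAP Table 3.

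If no NHL subject is in the response evaluable population, one sentence in Section 13 saying so is enough. If RECIST is meant to replace IWG, Section 13 should declare that and give the reason.

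The cost is SAP wording, output titles and at most one derivation branch. No new data are needed if sites recorded responses as the protocol directs.

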**Table 3: Confirmed Response per RECIST 1.1**

Initial Response	Subsequent Timepoint	Confirmed Response
Complete Response (CR)	CR at least 4 weeks after initial CR (or consecutive CRs with at most one NE in between with the last CR at least 4 weeks after initial CR)	CR
	CR less than 4 weeks	SD

Initial Response	Subsequent Timepoint	Confirmed Response
	PD or Not Evaluable (NE) or no subsequent assessment	SD if CR is at least 6 weeks from Cycle 1 Day 1, otherwise PD or NE
Partial Response (PR)	PR/CR at least 4 weeks after initial PR (or consecutive PRs/CRs with NEs in between with the last PR/CR at least 4 weeks after initial PR)	PR
	PR/CR less than 4 weeks, or SD	SD
	PD or NE or no subsequent assessment	SD if PR is at least 6 weeks from Cycle 1 Day 1, otherwise PD or NE
Stable Disease (SD)	PD or NE, SD, or no subsequent assessment	SD if SD is at least 6 weeks from Cycle 1 Day 1, otherwise PD or NE
Progressive Disease (PD)	Any assessment or no subsequent assessment	PD

The best overall confirmed response will be the best confirmed response from the above following the order of CR > PR > SD > PD > NE

The best overall response will be summarized for the following endpoints with count and percentage:

- CR
- PR
- SD
- PD
- NE
- ORR (CR + PR) with 95% CI (Wilson method [1])
- DCR (CR + PR + SD) with 95% CI (Wilson method)

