9.3 TUMOR RESPONSE

All subjects who have measurable disease, receive at least one cycle of SRA737 and have a baseline plus at least 1 post-baseline assessment of disease will be evaluable for response. Subjects who develop clear evidence of PD without a formal disease assessment and those without a formal disease assessment before study withdrawal will be considered non-responders. Complete responses and PRs are required to be confirmed by a subsequent assessment at least 4 weeks later. Stable Disease (SD) determination requires that the relevant criteria be met at least once, a minimum of 6 weeks after the initial dose of SRA737 is given.

Should rapid tumor progression occur before the completion of 4 weeks of treatment the subject will be classified as having early progression.

Tumor response should be classified as “not evaluable” (NE), only when it is not possible to classify it under another response category, for example, when baseline and/or follow-up assessment is not performed or not performed appropriately.

Expert reviewers appointed by the Sponsor may undertake an independent review of the investigator's assessed objective responses (CR and PR). Any independent reviewer's assessment will also be documented in the final clinical study report along with the assessment made by the investigator. The eCRF will reflect the investigator's opinion.

9.3.1 *RECORDING OF RESPONSE IN THE ECRF*

The applicable overall response category for each visit that includes disease assessment must be recorded in the eCRF.

9.3.2 *OTHER DEFINITIONS OF OUTCOME*

- **Toxic death:** Any death to which drug toxicity is thought to have a major contribution.
- **Early death:** Death during the first 28 days of treatment.

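### SAP Table 3 lets a PR be confirmed across any number of not-evaluable scans but a CR across only one, so a first-response CR can be scored SD and leave ORR where the same pattern starting from PR counts

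*SAP*

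**What the plan says.** SAP 11.1.1 asks for a repeat scan "not less than 4 weeks from the date the response was first documented", for PR and CR alike. Protocol 9.2 and 9.3 set the same 4-week minimum for both. None of these sections limits the number of NE scans in between.

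SAP Table 3 turns this into a derivation, and its two confirmation rows differ:

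- Initial CR: a CR at least 4 weeks later, or "consecutive CRs with at most one NE in between with the last CR at least 4 weeks after initial CR".
- Initial PR: a PR or CR at least 4 weeks later, or "consecutive PRs/CRs with NEs in between with the last PR/CR at least 4 weeks after initial PR".

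A CR that is not confirmed and is followed by PD, NE or nothing is scored "SD if CR is at least 6 weeks from Cycle 1 Day 1, otherwise PD or NE". The table has no route by which an unconfirmed CR counts as PR. Timepoints are then combined: "The best overall confirmed response will be the best confirmed response from the above", ranked CR, PR, SD, PD, NE. ORR counts confirmed CR and PR with a Wilson interval; DCR adds SD.

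On stable disease, protocol 9.3 states: "Stable Disease (SD) determination requires that the relevant criteria be met at least once, a minimum of 6 weeks" after the first dose. Most SD branches of Table 3 test 6 weeks from Cycle 1 Day 1. Two do not: the branch for a second CR inside 4 weeks, and the branch "PR/CR less than 4 weeks, or SD". Both return SD unconditionally.

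SAP section 13 lists five changes from the protocol. Neither an NE limit nor a change to the SD minimum is among them.

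**The concern.** The deeper response is held to the stricter rule. With an identical scan pattern, a subject who starts at CR can finish in a lower category than one who starts at PR, and two CRs well over 4 weeks apart can be reported as a non-response. The SAP gives no reason for the difference.

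ORR and DCR are endpoints under a primary objective, and Table 3 is the RECIST derivation that feeds both. The protocol also attaches meaning to an empty numerator: section 11.2.3 reads 0 responders in 20 as excluding an ORR of 16%. A single misclassified subject matters most there. A subject who loses confirmed response is also left out of TTR and DOR under SAP 11.1.2 and 11.1.3.

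The missing 6-week test works in the other direction: an early response that was never confirmed could enter DCR as SD without meeting the protocol's minimum.

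**Working it through.** **Plan's own figure.** Wilson limits are [p + z²/(2n) ± z√(p(1−p)/n + z²/(4n²))] / (1 + z²/n), with z = 1.960 (z² = 3.8415) and n = 20 (SAP section 7).

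- 0/20: the lower limit is 0; the upper is z²/(n + z²) = 3.8415/23.8415 = 0.161.
- 1/20: centre (0.05 + 0.0960)/1.1921 = 0.1225; half-width 1.960 × √(0.002375 + 0.002401)/1.1921 = 0.1136; limits 0.009 and 0.236.

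Both match the table in protocol 11.2.3, as do its other 19 rows.

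**Tracing Table 3.** Scans are placed every 8 weeks (protocol 7.2.2) at weeks 8, 16, 24, 32 and so on. Each timepoint is taken in turn as the initial response and the best result is kept.

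| Sequence | Result at each timepoint | Best confirmed | In ORR |
|---|---|---|---|
| CR-NE-CR | CR, NE, SD | CR | yes |
| PR-NE-PR | PR, NE, SD | PR | yes |
| CR-NE-NE-CR | SD, NE, NE, SD | SD | **no** |
| CR-NE-NE-CR-PD | SD, NE, NE, SD, PD | SD | **no** |
| PR-NE-NE-PR | PR, NE, NE, SD | PR | yes |
| PR-NE-NE-CR | PR, NE, NE, SD | PR | yes |
| PR-CR-NE-NE-CR | PR, SD, NE, NE, SD | PR | yes |
| CR-NE-NE-CR-CR | SD, NE, NE, CR, SD | CR | yes |

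In CR-NE-NE-CR, the first CR exceeds the one-NE limit and falls to SD. The last CR has nothing after it and is also SD. Both are past 6 weeks, so the subject counts in DCR but not in ORR.

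**Same allowance in both rows.** With no limit, CR-NE-NE-CR becomes CR and PR-NE-NE-PR stays PR. With a cap of one NE, both become SD.

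**Size.** One subject in 20 is 1/20 = 5 percentage points. If there are no other responders (an illustration), 0/20 with 0 to 16.1% is reported where the protocol's rule gives 1/20 with 0.9 to 23.6%.

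**6-week branches.** A scheduled scan falls at week 8 ± 1, so at week 7 or later, and passes the test. Extra scans are allowed when clinically indicated (protocol 9.2.2).

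- One early scan: PR at week 5, then PR or SD at week 8. The week-8 scan earns SD under a branch that does test 6 weeks, so SD is legitimate.
- Two early scans: PR at week 3, PR at week 5, PD at week 8. The first PR is followed by a PR only 2 weeks later, so it is SD with no test; the second is before week 6 and gives PD. Best confirmed response is SD, although no scan met the 6-week minimum.

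**The case against.** The best textual defence is that the opening clause of the CR row, a CR at least 4 weeks after the first, already covers CR-NE-NE-CR. Read that way, however, the limit of one NE would have no effect. The limit does some work only if the opening clause means the next assessment. The wording is at best ambiguous, and two programmers could code it differently, so it needs correcting on either reading.

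The objection on scope stands. A reader might infer that every subject with two NEs between CRs is lost. The trace does not support that: a PR before the CR, or another CR at least 4 weeks after the return to CR, keeps the subject in ORR. Nor do the documents support inferring a material downward bias in ORR across the trial. Loss needs a first-response CR, two consecutive NE scans, a return to CR and then no confirmation, and no rates are given for any of these. A reader might also infer that one early scan lets an unconfirmed response into DCR. It takes at least two scans before week 6 and no later qualifying non-PD scan.

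The consequence is also limited. SAP 9.1.2 calls the results supportive, no decision threshold is tied to ORR, and the listing of responses by timepoint would show an affected subject. SAP section 16 plans no TTR or DOR table, figure or listing. For mCRPC the protocol uses a composite with PSA and CTC, so Table 3 is not the only route to response there. These points lower the weight of the problem without making the rule consistent.

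Protocol Appendix 2, section 2.4.3, says confirmation is not required, which conflicts with protocol 9.2 and 9.3. It offers no defence here: under that statement too the subject would be a CR.

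**Conclusion.** The rule is wrong as written. Table 3 can score two CRs at least 4 weeks apart as a non-response, while the same pattern starting from PR is a response. It departs without explanation from the single 4-week rule in SAP 11.1.1 and protocol 9.2 and 9.3. The effect is 5 percentage points of ORR per affected subject in a cohort of 20, with no loss from DCR. Affected subjects should be rare and the analysis is descriptive, so this is a correction to make rather than a threat to the trial's conclusions.

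The conclusion rests on three readings: the plural NEs in the PR row means no maximum; the one-NE limit in the CR row is meant to have effect; and scans follow the 8-week schedule, so that a CR is past 6 weeks. The missing 6-week test is real but minor.

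**What to change.** Reword the CR row to match the PR row: allow intervening NE scans without a stated maximum, provided the last CR is at least 4 weeks after the first. This restores the protocol's rule.

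If the sponsor prefers a cap, state the same cap in both rows and list it in SAP section 13 as a change from the protocol. Equal wording alone does not rescue the CR subject: a cap of one would score both CR-NE-NE-CR and PR-NE-NE-PR as SD.

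No rule that a CR followed by PR counts as at least PR should be added. Appendix 2 of the protocol measures progression from the smallest sum on study and treats new lesions as progression, so reappearance after a CR may be PD.

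As a tidy-up, make the two unconditional SD branches require at least 6 weeks from Cycle 1 Day 1, tested at the latest qualifying non-PD scan, and otherwise return PD or NE.

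The cost is SAP wording and a few lines of analysis-dataset code. No new data are needed.
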